## 5. TREATMENT PLAN

### 5.1 Lapatinib Administration

Treatment will be administered on an outpatient basis. Reported adverse events and potential risks are described in Section 7. Appropriate dose modifications lapatinib

are described in Section 5.2 below. No investigational or commercial agents or therapies other than those described below may be administered with the intent to treat the patient's malignancy.

Lapatinib will be administered as an oral dose of 500 mg twice daily (in the morning and evening). All medications are given daily for 28 days, 28 days (4 weeks) equals one cycle. The first course will consist of 28 days (one cycle). All subsequent courses will consist of 2 cycles. Up to 27 cycles may be administered (14 courses, approximately 2 years).

Patients will be instructed to take the medications at the same time each day taken one hour before or after meals. Patients will be advised not to consume grapefruit or grapefruit juice while taking the study medications. The patient will be requested to maintain a medication diary of each dose of medication and any side effects and/or adverse events the patient may experience. The medication diary will be returned to clinic staff at the end of each course.

Prior to discharge from the clinic, the research nurse will review the following information with the patient:

- The toxicities of each agent and how to treat/prevent them
- The signs and symptoms to report to the study team
- How to complete the medication self administration record (patient diary)(See Appendix F for lapatinib-specific medication diary).
- Instructions to carefully observe for signs and symptoms of AEs
- Potential risks regarding pregnancy and fetal exposure
- Study agents should never be shared

Patients will be dispensed 1 cycle of drug at a time (Section 5.3.7). At each cycle prior to drug dispensing, the toxicity information as described in section 7 will be reviewed with the patient.

## 5.2 Dosing Delays/Modifications

General guidelines for treatment modifications at the time of re-treatment:

Adverse Events: All adverse events in this trial will be graded using the NCI Common Terminology Criteria for Adverse Events (CTCAE) version 4.0 - a complete listing is available at the CTEP website:  
<http://ctep.cancer.gov/forms/CTCAEv4.pdf>.

Dose adjustments will be made according to the guidelines below, with dose levels defined as follows:

Dose Level (DL)	Agent Dose
0	Lapatinib 500 mg twice daily
-1*	Lapatinib 1000 mg once daily

-2*	Lapatinib 750 mg once daily
-----	-----------------------------

\* The Cmax for lapatinib is higher when administered at a BID dose.

Please refer to Table 2 (background section) for specific values.

**Table 5** Summary of dose holding/interruptions and dose de-escalation recommendations for lapatinib in case of lapatinib-related adverse events (graded according to NCI-CTCAE v4.0)

General Adverse Events	Action
Non-hematological, Grade 1 or 2	Continue lapatinib therapy at full dose prescribed. Apply maximum supportive care recommendations. If prolonged duration of Grade 2 adverse event ( $\geq 7$ days) is affecting quality of life, decrease dose to DL -1, if symptoms persist and continue to affect quality of life for $\geq 7$ more days, a second dose reduction to DL -2 will be allowed.
Non-hematological, Grade 3 or 4 (excluding cardiac and hepatobiliary events)	Apply maximum supportive care recommendations. Hold lapatinib therapy until recovery to Grade $\leq 1$ (up to 14 days). For NCI-CTCAE v4.0 Grade 3 or 4 interstitial pneumonitis or Grade 4 rash manifested as toxic epidermal necrolysis (e.g. Stevens-Johnson Syndrome etc) lapatinib must be permanently discontinued If recurrence of adverse event after drug hold/interruptions is observed, and maximum supportive care measures applied, hold drug once again until recovery to Grade $\leq 1$ (up to 14 days) and restart drug at DL-1. If adverse event recurs, a second dose reduction to DL -2 will be allowed after symptoms recover to Grade $\leq 1$ .
Non-hematological, Grade 3 or 4 adverse events NOT resolved to Grade $\leq 1$ within a maximum of 2 weeks from last planned administration	Action (discontinue or resume lapatinib therapy) in individual cases after discussions with the Sponsor. Up to 2 reductions (DL-1 and DL-2) will be considered after maximum supportive care recommendations are introduced.
Cardiac Adverse Events	
Cardiac (Severity corresponding to NYHA criteria)	Lapatinib therapy to be discontinued permanently in case of symptomatic NYHA class III and IV CHF. Lapatinib therapy to be held, continued, or resumed according to Figure 9 (please see Section 5.2.1 below) for patients with NYHA class I or II CHF.
Hepatobiliary Adverse Events	
Grade 3 AST/ALT* and Grade 2 total bilirubin elevation	Hold lapatinib for 2 weeks; restart drug at DL-1 if events resolved to $\leq$ Grade 1. If Grade 3 events recur after dose reduction, then discontinue lapatinib.

Grade 2 AST/ALT or Grade 1 total bilirubin elevation	Hold lapatinib for 2 weeks and restart drug at full dose if events resolved to $\leq$ Grade 1.
Grade 4 events	Discontinue lapatinib
* retest within 3 days from the first occurrence and then weekly to determine if ALT elevation persists	
Note: In case of multiple short interruptions of dose due to either adverse events or drug supply or other reasons the sum of days without lapatinib treatment should not exceed 21 days in any 90 day treatment period.	

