### Pharmacokinetics

A number of phase I trials evaluating the pharmacokinetics of lapatinib have been conducted. In general, lapatinib is well tolerated without the need for dose adjustment up to 1,800 mg once daily and 500 mg twice daily.

Lapatinib serum concentrations increase

- Proportionally with increase in daily dose
- Repeat dosing
- When taken with food, in particular high-fat meals

The pharmacokinetic properties of lapatinib for once daily and twice daily dosing are summarized in Table 2 and discussed in the following paragraphs.

Dose	Cmax (mg/L)*		Cmin (mg/L)*		AUC T (h*mg/L)*	
	Geo. Mean †	Mean (SD) ‡	Geo. Mean †	Mean (SD) ‡	Geo. mean †	Mean (SD) ‡
175mg QD (n = 3)	0.37	0.41 (0.25)	0.17	0.17 (0.05)	5.48	5.86 (2.74)
375mg QD (n = 3)	0.41	0.44 (0.21)	0.19	0.21 (0.13)	5.74	6.23 (3.20)
675mg QD (n = 4)	1.06	1.14 (0.43)	0.3	0.35 (0.18)	13.7	14.34 (5.04)
900mg QD (n = 4)	1.05	1.06 (0.19)	0.31	0.33 (0.10)	12.7	12.8 (1.94)
1,200 mg QD (n = 5)	1.39	1.55 (0.87)	0.4	0.48 (0.31)	17.3	20.0 (12.3)
1,600 mg QD (n = 4)	1.92	1.97 (0.58)	0.45	0.45 (0.08)	22.7	23.0 (4.1)
1,800 mg QD (n = 9)	1.89	2.02 (0.78)	0.74	0.82 (0.41)	27.7	29.6 (11.8)
500mg BID (n = 6)	2.2	2.37 (0.87)	0.96	1.10 (0.58)	18.1	19.6 (8.2)
750mg BID (n = 6)	1.87	2.11 (0.90)	0.92	1.15 (0.76)	15.4	18.0 (9.4)
900mg BID (n = 5)	3.27	3.57 (1.57)	1.77	2.04 (1.10)	28.5	31.5 (14.5)
1,250 mg fasted	0.76	0.91 (0.52)	—	—	9.07	10.7 (6.4)
1,250 mg fed	2.44	2.54 (0.84)	—	—	27.3	29.5 (12.0)

\*Day 14 steady-state data for all but fasted/fed (single dose).

†Geometric mean.

‡Arithmetic mean (SD).

Table 2. Summary of pharmacokinetic data on different dosing regimens for lapatinib (from Burris HA. Clin Cancer Res 2009)

At the dose of 1,250mg daily, steady state geometric mean (95% confidence interval) values of Cmax were 2.43 mcg/mL (1.57 to 3.77 mcg/mL) and AUC were 36.2 mcg hr/mL (23.4 to 56 mcg.hr/mL).

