### Absorption

On administration of doses of 25, 100, or 175 mg, oral absorption is delayed by ~30 minutes and Tmax is 3 to 4 hours. Time-dependent increases in Cmax and AUC are detected at the higher doses (100 and 175 mg) but not at the lower dose.

At the FDA-approved dose of 1,250 mg/d, the steady-state Cmax and AUC are 2.54 µg/mL and 36.2 µg h/mL, respectively. Administering lapatinib in divided daily doses increased the steady-state AUC ~2-fold compared with the same total dose administered once daily (Fig. 3).

[figure not shown]

Fig 3. Steady state 24-h AUC for once daily dosing (fat curve; o) and twice daily dosing (thin curve; Δ) of lapatinib (from Burris HA. Clin Cancer Res 2009)

With multiple daily dosing of lapatinib, steady state was achieved within 6 to 7 days. Systemic exposure to lapatinib is increased when the drug was administered with food, the greatest effect occurring with a high-fat meal. The AUC was increased by 325% and 167% when taken with high- and low-fat meals, respectively. However, while administration with food increased bioavailability of lapatinib, there was also increased variability in drug concentration potentially leading to increased toxicity.

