#### GI Toxicity

In the sentinel phase 1 trial of lapatinib, the incidence of diarrhea has been found to increase at higher doses, not at higher serum concentrations, suggesting that this adverse effect is the result of unabsorbed drug. The development of rash did not appear to be dose or serum related.

In the twice daily dosing group, grade 3 diarrhea (total of 17%) was the limiting toxicity. None in the 500 mg twice daily group required dose reductions due to diarrhea. However, in the 900 mg twice daily and 750 mg twice daily group, 33 percent of patients required dose modifications. The frequency of diarrhea as the most common dose-limiting toxicity (DLT) of lapatinib following administration once (QD) and twice (BID) daily doses is shown in Fig. 4 (from Burris HA. Clin Cancer Res 2009).

[figure not shown]

Fig. 4 Grade 1, 2, and 3 diarrhea as the most common adverse event in relation to different doses and dosing schedules (from Burris HA. Clin Cancer Res 2009)

In general, diarrhea events with lapatinib are in the majority of cases of grade 1 and 2 severity. No fatal lapatinib-associated diarrhea events have been reported. Lapatinib-related diarrhea occurs early usually within the first two weeks of treatment. The median duration of diarrhea with lapatinib was 5 days, with 85% of patients requiring no dose adjustment or interruption, and only 2% discontinuing therapy due to diarrhea. In general, severe diarrhea did not occur with lapatinib-containing regimens when proactive monitoring and appropriate intervention was instituted in a timely manner.

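### The first dose reduction (level -1) keeps the daily dose at 1,000 mg, so for diarrhea it does not lower the quantity that the protocol says drives the event, while systemic exposure falls.

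*Combined protocol and SAP*

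**What the plan says.** Section 5.2 defines three levels: level 0 is "Lapatinib 500 mg twice daily", level -1 is "Lapatinib 1000 mg once daily" and level -2 is "Lapatinib 750 mg once daily". The only rationale given for the two lower levels is a footnote, "The Cmax for lapatinib is higher when administered at a BID dose", which sends the reader to Table 2 for values. Table 2 has no row for 1,000 mg or 750 mg once daily.

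Table 5 applies these levels to non-hematological events generally. A Grade 2 event that lasts at least 7 days and affects quality of life leads to level -1. A Grade 3 or 4 event that recurs after a hold leads there too. Level -1 is also the restart level for one class of hepatobiliary events. Diarrhea has no separate rule in Table 5, and Appendix K suggests considering a reduction for Grade 2 diarrhea without naming a level.

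Section 2.2 bears on this in three places:
- GI Toxicity: in the phase 1 trial, diarrhea was found to "increase at higher doses, not at higher serum concentrations, suggesting that this adverse effect is the result of unabsorbed drug". The same text calls diarrhea the most common dose-limiting toxicity and says that rash did not appear related to dose or serum level.
- Absorption: "Administering lapatinib in divided daily doses increased the steady-state AUC ~2-fold compared with the same total dose administered once daily".
- Pharmacokinetics: serum concentrations rise "Proportionally with increase in daily dose".

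**The concern.** A dose reduction should lower whatever is thought to cause the toxicity. For diarrhea the protocol names dose and sets serum concentration aside, yet the first reduction leaves the daily dose where it was and changes the schedule, which mainly changes serum concentration. The footnote's Cmax argument therefore relies on the very quantity that GI Toxicity says does not drive diarrhea.

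Two things are at stake. A patient reduced for persistent diarrhea might get no relief from the step, by the protocol's own reasoning. The same patient would also lose part of the exposure for which 500 mg twice daily was chosen: section 2.2 justifies that regimen by its high Cmax and Cmin.

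**Working it through.** **1. Daily dose and single intake (section 5.2).**
- Level 0: 2 x 500 = 1,000 mg a day, 500 mg per intake.
- Level -1: 1 x 1,000 = 1,000 mg a day, 1,000 mg per intake. Change in daily dose: 0%.
- Level -2: 1 x 750 = 750 mg a day. Change from level -1: 1 - 750/1,000 = 25% lower.

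This needs no modelling. Step 1 does not lower daily dose; step 2 does.

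**2. Reproducing the ~2-fold statement, to learn how to read the AUC column of Table 2.** Inputs are Table 2 geometric means, with linear interpolation between neighbouring once-daily rows where a dose is missing.
- 1,000 mg once daily: 12.7 + (100/300) x (17.3 - 12.7) = 14.2
- 1,500 mg once daily: 17.3 + (300/400) x (22.7 - 17.3) = 21.35
- 1,800 mg once daily: 27.7 (a table row)

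If the twice-daily AUC covers a 12-hour interval, it must be doubled to give 24 hours:
- 500 mg twice daily: 2 x 18.1 / 14.2 = 2.54
- 750 mg twice daily: 2 x 15.4 / 21.35 = 1.44
- 900 mg twice daily: 2 x 28.5 / 27.7 = 2.06

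The geometric mean is 1.96, which matches the protocol. Without doubling, the ratios are 1.27, 0.72 and 1.03 (geometric mean 0.98), which does not match. The 12-hour reading is therefore the likely one, but it remains an assumption.

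**3. Exposure change from level 0 to level -1.**

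| Basis | Level 0 | Level -1 | Fall |
|---|---|---|---|
| AUC, ~2-fold statement | 2 | 1 | about 50% |
| AUC, Table 2 interpolated | 36.2 | 14.2 | 61% |
| AUC, 1,200 mg row as bound | 36.2 | 17.3 | 52% |
| AUC, 900 mg row as bound | 36.2 | 12.7 | 65% |
| Cmin, interpolated | 0.96 | 0.34 | 65% |
| Cmax, interpolated | 2.2 | 1.16 | 47% |

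Three curves fitted to all once-daily rows, weighted by row size (log-log, straight line, proportional through the origin), give AUC falls of 55-58%, Cmin falls of 58-61% and Cmax falls of 44-49%. If the twice-daily AUC were not doubled, the AUC fall would be only 10-21%.

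**4. A conflicting figure.** The Pharmacokinetics and Absorption text gives a steady-state AUC of 36.2 for 1,250 mg daily. Table 2 gives 17.3 for 1,200 mg once daily, less than half as much. Scaling 36.2 in proportion gives 36.2 x 1,000/1,250 = 29.0 at level -1, a fall of 1 - 29.0/36.2 = 20%.

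**5. How many patients.** Table 3 gives any-grade diarrhea of 25/69 = 36% on 500 mg twice daily: 0.36 x 25 = 9 patients. GI Toxicity says that 85% needed no dose adjustment or interruption, which leaves 15%: 9 x 0.15 = 1.35, so one or two of 25. This reads the 15% as a share of patients with diarrhea, and it counts interruptions as well as reductions.

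**The case against.** The strongest reply is that the schedule change is deliberate. The footnote shows an intent to lower Cmax, the levels serve events other than diarrhea, and for an exposure-driven event level -1 does reduce exposure. That stands for those events, but the protocol does not say which they are.

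Table 3 also weakens the premise. Diarrhea was 35% on 1,500 mg once daily and 36% on 500 mg twice daily, with Grade 3 in 1/69 and 3/69. A daily dose 50% higher, in one intake, did not produce more diarrhea. This could support a once-daily switch, but section 5.2 does not make that argument, and it sits uneasily with GI Toxicity. The sponsor should weigh it. It also answers a reader who might infer that level -1 would make diarrhea worse: the documents do not show that.

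Three further inferences go too far:
- **That the whole reduction scheme fails, because level -2 barely differs from level -1 in exposure.** Interpolation gives an AUC fall of only 6% (14.2 to 13.4), but it runs through the 675 and 900 mg rows, with 4 patients each, where AUC goes backwards (13.7, then 12.7). Log-log and straight-line fits to all once-daily rows give 19-22%, and the stated proportionality gives 25%. Level -2 also lowers daily dose.
- **That about 9 of 25 patients would be affected.** That counts any-grade diarrhea. Table 5 needs prolonged Grade 2 or recurrent or unresolved Grade 3-4 events, median duration is given as 5 days, and no one on 500 mg twice daily is reported to have needed a reduction for diarrhea.
- **That the response rate must be analysed by dose level.** Dose level at a scan is a post-treatment variable, and one or two reduced patients would tell little. Section 12.5.2 already keeps all eligible treated patients in the main analysis.

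**Conclusion.** The point holds for the first step. Level -1 is the same daily dose as level 0 with each intake doubled, so a reduction made for diarrhea does not lower the quantity that GI Toxicity holds responsible, and the Cmax footnote does not cover that event. This part rests on section 5.2 and section 2.2 alone.

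The size of the exposure loss is less certain: about half on the ~2-fold statement, and about 52-65% for AUC from Table 2 on the 12-hour reading, with Cmin down 58-65% and Cmax about 47%. A flat claim that exposure falls by more than half is not supported: Cmax does not, the ~2-fold statement gives only about half, and the 1,250 mg figure would imply about 20%. Table 2 and that figure cannot both describe the same relation and need reconciling.

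The reach through diarrhea is small, probably one or two of 25 patients. The plan should still be corrected, because investigators who follow Table 5 as written will carry the contradiction out.

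**What to change.** Reconcile the dose-level table and Table 5 in section 5.2 with the Pharmacokinetics (including Table 2), Absorption, Toxicity Profile (Table 3) and GI Toxicity parts of section 2.2. For diarrhea, and for each other event class in Table 5, state whether the first step is meant to lower daily dose or systemic exposure, and confirm from the cited data that the level does so. Resolve the AUC of 36.2 at 1,250 mg daily against 17.3 at 1,200 mg once daily, and state the interval that the AUC column of Table 2 covers. Which dose or rule to adopt is a clinical decision, and none is proposed here.

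Optionally, list the dose level in force for each responder as a description only, without a separate response-rate analysis.

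The cost is protocol wording and, if wanted, one listing. No extra patients, visits or tests are needed.

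### Table 5's hepatobiliary dosing rows are ambiguous, leave some liver-test grades without a row, and conflict with the table's general rows

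*Combined protocol and SAP*

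**What the plan says.** Table 5 in Section 5.2 has three hepatobiliary rows.

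- **Row 1** is triggered by "Grade 3 AST/ALT* and Grade 2 total bilirubin elevation". Its action begins "Hold lapatinib for 2 weeks; restart drug at DL-1 if events resolved to" Grade 1 or less, and it adds "If Grade 3 events recur after dose reduction, then discontinue lapatinib". The asterisk on AST/ALT leads to a footnote: "retest within 3 days from the first occurrence and then weekly to determine if ALT elevation persists".
- **Row 2** is triggered by "Grade 2 AST/ALT or Grade 1 total bilirubin elevation". Its action is "Hold lapatinib for 2 weeks and restart drug at full dose if events resolved to" Grade 1 or less.
- **Row 3** discontinues the drug for Grade 4 events.

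Three general non-hematological rows stand above these.

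- The Grade 1–2 row continues treatment at full dose with supportive care. It allows reductions for prolonged Grade 2 events that affect quality of life, and it has no hepatobiliary exclusion.
- The Grade 3–4 row is limited by the words "excluding cardiac and hepatobiliary events".
- The row for Grade 3–4 events unresolved after two weeks refers individual cases to discussion with the Sponsor. It does not repeat the exclusion.

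A note under the table caps time off drug at 21 days in any 90-day treatment period.

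**The concern.** Rows 1 and 2 are adjacent and differ in their conjunction, so a site may take the difference as deliberate. On that reading a more severe transaminase rise can lack a dosing instruction that a milder one has. The row that would normally catch a Grade 3 event excludes hepatobiliary events. Separately, a hold triggered at Grade 1 bilirubin ends on a test that Grade 1 already passes.

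The protocol itself treats liver events with care. Section 7.1 lists hepatic failure as rare but serious. Section 3.2.4 admits patients with liver metastases. Section 5.9 follows hepatobiliary events to Grade 1, where other events are followed to Grade 2. In a multicentre trial with 25 evaluable patients at most, what is at stake is that sites may handle the same laboratory result differently, with consequences for patient safety and for dose exposure.

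**Working it through.** The plan gives no figure to reproduce, so the check sets every grade combination against the rows.

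**Inputs.** The triggers and actions of the three hepatobiliary rows, the general rows and the 21-in-90-day cap, all from Table 5.

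**Step 1: enumerate.** AST/ALT grade 0–4 by bilirubin grade 0–4 gives 5 × 5 = 25 pairs. Four have both values at Grade 0 or 1, so 25 − 4 = 21 have at least one value at Grade 2 or above. The pairs that matter are these:

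| AST/ALT grade | Bilirubin grade | 'and' means both | 'and' means either |
|---|---|---|---|
| 2 | 0 | row 2 | row 2 |
| 3 | 0 | none | row 1 |
| 3 | 1 | row 2 only | rows 1 and 2 |
| 3 | 2 | row 1 | row 1 |
| 3 | 3 | none | row 1 |
| 2 | 2 | row 2 | rows 1 and 2 |
| 0 or 1 | 1 | row 2 | row 2 |
| 0 or 1 | 2 | none | row 1 |
| 0 or 1 | 3 | none | none |

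Pairs at Grade 2 or above with no hepatobiliary row, written (AST/ALT, bilirubin):

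- 'Both': (3,0), (3,3), (0,2), (1,2), (0,3), (1,3), which is 6 of 21.
- 'Either': (0,3), (1,3), which is 2 of 21.

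**Step 2: check the order of severity under 'both'.** Grade 2 AST/ALT alone triggers a hold; Grade 3 alone matches no row. Grade 3 AST/ALT with Grade 1 bilirubin enters only row 2, through its bilirubin trigger, and so restarts at full dose. Bilirubin alone triggers a hold at Grade 1 but matches no hepatobiliary row at Grade 2, where only the general continue row applies.

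**Step 3: check the 'either' reading.** It closes the gaps in Step 2. Isolated Grade 3 bilirubin still has no row. The pairs (3,1) and (2,2) now meet both row 1 and row 2, which restart at different doses, and the table does not say which row governs.

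**Step 4: general row against row 2.** Both row 2 triggers, Grade 2 AST/ALT and Grade 1 bilirubin, are themselves non-hematological Grade 1 or 2 events. The general Grade 1–2 row continues them at full dose; row 2 holds them for two weeks. The conflict covers every event that enters row 2 and does not depend on how 'and' is read.

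**Step 5: row 2 restart condition.** For Grade 2 AST/ALT, Grade 1 or less is a real test. For Grade 1 bilirubin it is true on the first day of the hold and can fail only if the value worsens. If bilirubin is still Grade 1 after two weeks, the restart condition and the hold trigger are both met.

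**Step 6: the cap.** One hold is 14 days, within 21. Two holds within 90 days are 14 + 14 = 28 days, which is 28 − 21 = 7 days above the cap. This assumes that a site treats the persisting Grade 1 value as a fresh trigger.

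**The case against.** The strongest reply is that row 1's 'and' joins two separate triggers in a list. Row 1 itself supports this. Its recurrence clause speaks of Grade 3 events, and AST/ALT is the only Grade 3 item in the row. The footnote follows ALT alone. This reading is credible, so a reader who infers that the protocol definitely has no rule for an isolated Grade 3 AST/ALT rise goes further than the text allows. But the protocol does not state this reading, and row 2's 'or' points the other way.

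Even on the literal reading, such a patient is not without any provision. The footnote requires a retest. The row for unresolved Grade 3–4 events could later bring in Sponsor discussion. Section 5.8 lists unacceptable adverse events and investigator judgment as reasons to stop treatment. Table 5 calls itself a set of recommendations for lapatinib-related events. All of this stands, but none of it gives a dosing action at onset.

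On the Grade 1 bilirubin hold, its length is fixed at two weeks, so the instruction for a first event is determinate. Only the restart test is empty. It could also be said that a specific row overrides a general one. That is a reasonable convention, but the table writes an exclusion into the general Grade 3–4 row and none into the Grade 1–2 row.

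A reader might also infer that the safety tabulation is distorted. The documents do not support that. Events are graded by CTCAE version 4.0 whatever is done with the dose, and Section 12.5.1 makes all treated patients evaluable for toxicity. Nor can the number of affected patients be estimated: Section 7.1 puts AST, ALT and bilirubin increases in a band of up to 20% without separating grades, and gives no rate for this population.

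**Conclusion.** The point holds as an ambiguity and internal inconsistency in Table 5. Three faults do not depend on how 'and' is read: isolated Grade 3 bilirubin has no row; the general Grade 1–2 row contradicts row 2; and the restart condition after a Grade 1 bilirubin hold is met at its trigger. The missing dosing action for isolated Grade 3 AST/ALT, the milder handling of Grade 3 AST/ALT with Grade 1 bilirubin, and the missing row for isolated Grade 2 bilirubin all depend on 'and' meaning both.

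The size is 6 of 21 grade pairs without a hepatobiliary row on the literal reading and 2 of 21 on the list reading. These are counts of table cells, not of patients. The count takes Grade 4 in either test as enough for row 3. The matter concerns consistent handling of patients and dose exposure. It does not undermine the primary response analysis, because Section 12.5.2 keeps eligible patients in that analysis despite deviations in drug administration.

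**What to change.** Reconcile the hepatobiliary and general rows of Table 5:

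1. State whether 'and' in row 1 means both events or either.
2. Make every AST/ALT and bilirubin grade, alone or combined, fall in exactly one row.
3. Exclude hepatobiliary events from the general rows wherever a specific row applies, including the Grade 1–2 row and the row for unresolved events.
4. Give each hold a restart condition that is not already met at its trigger, and check repeated holds against the 21-in-90-day cap.

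The clinical team must set the actions; no dose or rule is proposed here. The cost is an amendment to one table, with no change to sample size, endpoints or analysis.

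### Table 5 restarts lapatinib at full dose at the same bilirubin grade that triggered the hold, so a Grade 1 elevation need not improve

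*Combined protocol and SAP*

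**What the plan says.** The hepatobiliary part of Table 5 (section 5.2) has two hold rows.

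- The upper row covers Grade 3 AST/ALT with Grade 2 total bilirubin. Its action is "Hold lapatinib for 2 weeks; restart drug at DL-1 if events resolved to" Grade 1 or less.
- The lower row covers "Grade 2 AST/ALT or Grade 1 total bilirubin elevation". Its action is "Hold lapatinib for 2 weeks and restart drug at full dose if events resolved to" Grade 1 or less. One restart level serves both triggers.

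A footnote attached to Grade 3 AST/ALT in the upper row asks sites to "retest within 3 days from the first occurrence and then weekly to determine if ALT elevation persists". It sets nothing for bilirubin. A note under the table limits interruptions: "the sum of days without lapatinib treatment should not exceed 21 days in any 90 day treatment period". The row that sends unresolved events to the Sponsor for discussion is confined to "Non-hematological, Grade 3 or 4 adverse events NOT resolved to Grade" 1 or less within 2 weeks, so it does not reach Grade 1 bilirubin.

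Eligibility criterion 3.1.9 requires total bilirubin inside the institution's normal range at entry. An on-study Grade 1 value is therefore a change from a normal baseline.

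**The concern.** A hold with a restart condition normally asks for some recovery before the drug is given again. For Grade 1 bilirubin this row asks for none: a patient whose value has not moved goes back to the full dose at the level that caused the stop. Read literally, the row then calls for a second hold when the same value is next seen, and that second hold collides with the table's own limit on days off drug. Sites could reasonably differ. One may keep dosing at a level the table says to hold, another may hold past the cap, and a third may stop treatment. At stake are a dosing-safety rule and its consistent use across sites, not the trial's statistical operating characteristics.

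**Working it through.** The plan states no figure to reproduce here. The check compares triggers with restart levels and then counts days.

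**Trigger against restart level (Table 5, hepatobiliary rows)**

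| Row | Trigger | Restart level | Recovery needed? |
|---|---|---|---|
| Upper | AST/ALT Grade 3 | Grade 1 or less | Yes, 3 > 1 |
| Upper | Bilirubin Grade 2 | Grade 1 or less | Yes, 2 > 1 |
| Lower | AST/ALT Grade 2 | Grade 1 or less | Yes, 2 > 1 |
| Lower | Bilirubin Grade 1 | Grade 1 or less | No, 1 ≤ 1 |

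Only the last condition is already met on the day the hold starts.

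**Is a bilirubin restart level set elsewhere?**

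- The retest footnote concerns ALT.
- The Sponsor-discussion row concerns Grade 3 or 4 events.
- Section 5.9 follows hepatobiliary events to Grade 1 or less, so it is no stricter.
- Sections 5.3.7 and 5.8 leave continuation to judgment and name no level.

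**Days off drug if Grade 1 persists**

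Inputs: nominal laboratory visits at day 14 (5.3.2), day 28 (5.3.3) and day 42 (5.3.4, day 14 of cycle 2), counting day 0 as the first dose; hold length 14 days; cap 21 days in any 90. Assume the first Grade 1 value is on day 14 and does not change.

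- First hold: days 14 to 27 = 14 days. Full dose resumes on day 28.
- Day 42: still Grade 1, so the trigger is met again. Second hold: days 42 to 55 = 14 days.
- Total: 14 + 14 = 28 days off drug between days 14 and 55, well inside one 90-day period.
- Excess over the cap: 28 − 21 = 7 days. Day 48 is the 21st held day, and the cap is passed on day 49.
- Room under the cap after the first hold: 21 − 14 = 7 days.

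**Link with the upper row**

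A patient restarted at dose level −1 with bilirubin at Grade 1 satisfies the upper row. That patient already stands at the lower row's hold trigger, and the lower row's restart is at full dose.

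**Reach**

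Section 7.1 lists blood bilirubin increase in the column for 20% or less. Section 2.2 reports that, in the first-line breast cancer trial, each related event outside the four most frequent occurred in under 10% of patients. Applied to 25 patients, these give at most 0.20 × 25 = 5 and under 0.10 × 25 = 2.5 patients with any bilirubin event. Neither source gives the share that is Grade 1 and still present after 2 weeks off drug, so the number meeting the rule cannot be derived.

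**The case against.** The strongest reply is that the row works as a fixed washout followed by rechallenge. Section 2.2 gives a half-life of about 24 hours on repeated dosing, so 14 days is about 14 half-lives. A Grade 1 value unchanged after that points towards another cause, such as liver metastases or Gilbert's syndrome, both of which 3.2.4 allows. Table 5 applies only to lapatinib-related events and is offered as guidance. Under 5.3.7 the latest laboratory data are reviewed before each cycle's drug is dispensed; in the example above, that review falls at the day-28 restart. Section 5.8 lets the investigator stop treatment, and the study calendar allows extra assessments. Section 5.9 also treats Grade 1 or less as resolution.

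Much of this stands, and it lowers the risk to patients. It does not supply the missing level. If washout and rechallenge was intended, the table should say so and say what follows when Grade 1 persists. The word resolved may suggest improvement, but the written endpoint accepts an unchanged value. Section 5.9 governs when follow-up may end, which is a different question from when to re-expose.

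Some stronger readings are tempting but not supported:

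- **That the table is silent at the next Grade 1 value.** Read literally, it says hold again. The gap is what to do when that hold runs into the cap.
- **That Grade 1 bilirubin carries two equal, contradictory instructions.** The general Grade 1 or 2 row says "Continue lapatinib therapy at full dose prescribed" and lacks the exclusion found in the next row ("Non-hematological, Grade 3 or 4 (excluding cardiac and hepatobiliary events"). But it sits under the general heading, and the specific hepatobiliary row governs on ordinary reading.
- **That patients return to full dose unchecked.** Sections 5.3.7 and 5.8 require or permit review.

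**Conclusion.** The point holds as a narrow, minor defect in a dosing-safety rule. For one of the four hepatobiliary triggers, Grade 1 bilirubin, the restart condition demands no recovery. It can fail only through worsening bilirubin or AST/ALT above Grade 1. A persistent value leads to a second hold and 28 days off drug against a cap of 21, with no rule for resolving the conflict. The 28-day figure assumes nominal visit days, an unchanged Grade 1 value and a full second 14-day hold.

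The number of patients affected is probably small but cannot be quantified from the documents. A reader might want the chance of at least one case among 25 patients, but any such figure would rest wholly on an assumed frequency and should carry no weight. Nor do the documents support an inference that power, the response denominator or the two-stage decision rule is affected.

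**What to change.** In the lower hepatobiliary row, split the restart condition: resume full dose when AST/ALT is at Grade 1 or less **and** total bilirubin is back in the institution's normal range, the limit already used in 3.1.9. Add that, if bilirubin is not normal at 2 weeks, the choice between resuming and discontinuing is made after discussion with the Sponsor and before the 21-day cap is reached, which leaves 7 days.

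In the upper row, either state that a Grade 1 bilirubin at restart on dose level −1 does not by itself trigger the lower row, or apply the same normal-range limit. Adding the hepatobiliary exclusion to the general Grade 1 or 2 row would be tidy but is not needed to close the gap.

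The cost is a few clauses in one table, with no change to sample size or scheduled visits. The downside is that some holds will last longer, including in patients whose elevation comes from Gilbert's syndrome or liver metastases. The Sponsor discussion is the route for those cases.
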